is present either by histopathological examination or by CT scan/MRI, repeat treatment cycles may be given 2-4 weeks after surgery, if the surgical incision has healed, and if the patient has ≤ grade I toxicity.

Resected or biopsied tumors will be analyzed for the effects of this dual therapy on disease control rate, and immune cell trafficking in the tumor microenvironment. Fresh and paraffin embedded tissue blocks will be analyzed by FACS for PD-L1 and other biomarkers, including Tregs, CD8+, CD4+ cells etc. Immunohistochemistry for cyclin G1, cyclin D1 and Ki67 will be conducted to determine the tumor's proliferative state. Histopathologic examination for tumor necrosis and mitotic index will also be determined.

Conditions for Continuation of Treatment in the Presence of Increased Tumor Size by CT scan or MRI Indicating Progressive Disease by RECIST v1.1:

Treatment may be continued if:

1. There are no signs or symptoms indicating unequivocal progression.
2. There is no worsening of ECOG score attributable to progressive disease.
3. There is no tumor growth at critical sites that is life-threatening.
4. Patient signs an informed consent that he/she is aware of alternative therapies but wishes to defer these therapies.
5. There is clinical benefit, as determined by investigator

Sample Size

40-50 patients may be enrolled. Patients who fail to become evaluable for the secondary endpoint with a follow-up CT/MRI will be replaced.

Study Population

Histology of Ewing's sarcoma, PEComa, epithelioid sarcoma, desmoid tumor, chordoma, non-small cell lung cancer, small cell lung cancer, urethelial carcinoma, melanoma, renal cell carcinoma, squamous cell carcinoma of head and neck, hepatocellular carcinoma, classical Hodgkin's lymphoma, MSI-H/dMMR metastatic colorectal cancer, and tumors with genetic mutations sensitive to mTOR inhibitors, will be confirmed locally by the institution prior to enrollment.

Patient Eligibility

Inclusion Criteria

A patient will be eligible for inclusion in this study only if all of the following criteria are met:

1. Patients must have a histologically confirmed diagnosis of Ewing's sarcoma, PEComa, epithelioid sarcoma, desmoid tumor, chordoma, non-small cell lung cancer, small cell lung cancer, urethelial carcinoma, melanoma, renal cell

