1.2. ABI-009 Background

1.2.1. Rapamycin and Rapalogs

Rapamycin is a crystalline powder with the empirical formula C51H79NO13 and a molecular weight of 914.17. Rapamycin is a protein kinase inhibitor that is approved for immunosuppression in renal transplant patients, and is under investigation as a cancer treatment. Rapamycin inhibits the mammalian target of rapamycin, mTOR, a regulatory protein kinase in cancer that recognizes high stress levels, including depleted nutrient levels and states of hypoxia (29). mTOR is a serine/threonine-specific protein kinase, downstream of the phosphatidylinositol 3-kinase (PI3K)/Akt (protein kinase B) pathway, and a key regulator of cell survival, proliferation, stress, and metabolism. Additionally, mTOR is involved in regulating angiogenesis by controlling endothelial and smooth muscle cell proliferation via the hypoxia-inducible factor-1 α and vascular endothelial growth factor (30). Consistent with its role in cell proliferation, the mTOR pathway is frequently overactivated in a number of human malignancies, and is thus considered to be an attractive target for anti-cancer therapy. Rapamycin and its analogs (rapalogs) function as allosteric inhibitors of mTORC1. Rapalogs are currently used in the treatment of advanced renal cell carcinoma and other tumors (31).

Numerous preclinical studies have reported the impact of different biomarkers involved in the mTOR pathway, on the efficacy of mTOR inhibitors, such as:

- PI3K, TSC1, TSC2, PI3K, AKT, and PTEN gene mutations (32)
- Phosphorylated p-AKT, p-S6, p-4EBP1 expression (33)
- biomarkers for the proliferation (Ki-67) and apoptosis (PARP) (31)

However, no clinical studies have confirmed the importance of these biomarkers as predictive factors of efficacy, except PI3K mutation in non PEComa tumors such as breast carcinoma (32).

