2.2.3. Exploratory Endpoints

- Correlation between DCR based on Immune-related Response Criteria (irRECIST) with that based on RECIST v1.1.
- Correlation between DCR with PD-L1 and other biomarker expression in patients' tumors.
- Correlation between DCR and PTEN mutation in patient's archived tumor

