3.2. Inclusion Criteria

A patient will be eligible for inclusion in this study only if all of the following criteria are met:

1. Patients must have a histologically confirmed diagnosis of Ewing's sarcoma, PEComa, epithelioid sarcoma, desmoid tumor, chordoma, non-small cell lung cancer, small cell lung cancer, urethelial carcinoma, melanoma, renal cell carcinoma, squamous cell carcinoma of head and neck, hepatocellular carcinoma, classical Hodgkin's lymphoma, MSI-H/dMMR metastatic colorectal cancer, and tumors with genetic mutations sensitive to mTOR inhibitors, that is either metastatic or locally advanced and for which surgery is not a recommended option.
2. Patients must have one or more measurable target lesions by CT scan or MRI. Measurable disease by RECIST v1.1, confirmed by investigator.
3. Previously treated patient with Ewing's sarcoma, PEComa, epithelioid sarcoma, desmoid tumor, chordoma, non-small cell lung cancer, small cell lung cancer, urethelial carcinoma, melanoma, renal cell carcinoma, squamous cell carcinoma of head and neck, hepatocellular carcinoma, classical Hodgkin's lymphoma, MSI-H/dMMR metastatic colorectal cancer, and tumors with genetic mutations sensitive to mTOR inhibitors, if treatment is completed after 5 half-lives or ≥ 28 days prior to enrollment, whichever is shorter.
4. Eligible patients, 12-17 years (≥ 40 kg) or 18 years old or older, with Eastern Cooperative Oncology Group (ECOG) performance status 0 or 1.
5. Patients must have the following blood chemistry levels at screening (obtained ≤ 14 days prior to enrollment (local laboratory):
 - a. total bilirubin $\leq 1.5 \times$ upper limit of normal (ULN) mg/dl

- b. AST/ALT $\leq 2.5 \times$ ULN ($\leq 5 \times$ ULN if attributable to liver metastases); alk phos $< 3 \times$ ULN (patients with alk phos > 3 ULN will be allowed if due to bone metastases) AST $\leq 2.5 \times$ ULN ($\leq 5 \times$ ULN if attributable to liver metastases)
- c. serum creatinine $\leq 1.5 \times$ ULN

6. Adequate biological parameters as demonstrated by the following blood counts at screening (obtained ≤ 14 days prior to enrollment, local laboratory):

- a. Absolute neutrophil count (ANC) $\geq 1.5 \times 10^9/L$; b. Platelet count $\geq 100,000/mm^3$ ($100 \times 10^9/L$); c. Hemoglobin ≥ 9 g/dL.

7. Serum triglyceride < 300 mg/dL; serum cholesterol < 350 mg/dL.

8. Male or non-pregnant and non-breast feeding female:

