4. TABLE OF EVENTS

The schedule of assessments in Table 2 outlines the specific time points for study assessments.

Table 2. Schedule of Assessments

Assessment ^a	Screening ^b (Day -14 to -1)	Cycle 1 through Last Cycle (Treatment Period)			End of Treatment (EOT) Visit ^d	Follow-up Period ^e
		Day 1 ^c	Day 8	Day 15		
General Assessments						
Informed Consent	X					
Demographics	X					
Medical History	X					
Physical Examination	X	X			X	
Vital Signs, Height and Weight	X	X ^f	X ^f	X ^f	X ^f	
BSA Calculation		X ^j				
Prior/Concomitant Medication Evaluation ^g	X	X	X	X	Until 28 days after the last dose of IP	
Prior/Concurrent Procedures Evaluation ^g	X	X	X	X	Until 28 days after the last dose of IP	
ECOG PS	X	X			X	
Pregnancy Test ^h	X				X	
ECG (12 lead) ⁱ	X					
Survival status						X
Adverse Events		Continuous starting from signing of Informed Consent until 28 days after last dose of IP				
Dexamethasone (every cycle)			X			
Nivolumab Dosing		X				
ABI-009 Dosing: To Start after 2nd Nivo dose			X	X		
Local Laboratory Assessments						
Clinical Chemistry Panel	X	X	X	X	X	
CBC, Differential, Platelet Count	X	X	X	X	X	

Assessment ^a	Screening ^b (Day -14 to -1)	Cycle 1 through Last Cycle (Treatment Period)			End of Treatment (EOT) Visit ^d	Follow-up Period ^e
		Day 1 ^c	Day 8	Day 15		
PT, PTT, INR	X					
Urinalysis	X					
Thyroid function	X	X				
HIV, HBV sAg, HBV cAb, HCV Ab	X					
Fasting Lipids	X	X				
Trough rapamycin level ^k						
Immunohistochemistry for PTEN mutation in archived tumor	X					
Imaging and Efficacy Assessments						
CT/MR ^l	X	Every 6 weeks after C1 D1 for the first year, then every 12 weeks thereafter			X	

- a. Unless otherwise specified, visits must occur within \pm 2 days of the planned visit date.
- b. Screening evaluations to be obtained \leq 14 days prior to enrollment unless specified otherwise.
- c. Day 1 evaluations can be omitted if screening evaluations are performed within 72 hours of Cycle 1 Day 1 except for thyroid and fasting lipids every 12 weeks.
- d. End of Treatment Visit must occur at least 4 weeks (\pm 7 days) after the last dose of ABI-009.

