- Local Laboratory Assessments: chemistry, complete blood count (CBC), differential, platelet count, coagulation, urinalysis, thyroid function, pregnancy

test (women of child-bearing potential, includes tubal ligations), HIV, hepatitis B surface antigen, hepatitis C antibody, fasting lipids

- Urinalysis (a urine dipstick may be used)
- CT or MRI, must be performed within 2 weeks prior to study day 1, preferably as close to the day of enrollment as possible
- Immunohistochemistry for PTEN mutation on patient's archived tumor

A patient is considered enrolled when the investigator decides that the patient has met all eligibility criteria. The investigator is to document this decision and date, in the patient's medical record and in/on the electronic case report form (CRF).

All screening tests and procedures must be performed within 14 days of study day 1, unless specified otherwise in the study procedures listed in [Section 4](#).

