8.4. Exploratory Analysis

DCR based on RECIST v1.1 will be correlated with DCR based on Immune-related Response Criteria (irRECIST) and summarized by descriptive statistics and comparative KM analysis.

PD-L1 and other biomarker expression in patients' tumors will be correlated with DCR and summarized by descriptive statistics.

DCR will be correlated with presence of PTEN mutation in patient's archived tumor and summarized by descriptive statistics.

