12.4 Research Use of Fresh and Stored Human Samples, Specimens or Data

- Intended Use: Samples and data collected under this protocol will be used to study the effects of combination therapy with ABI-009, an mTOR inhibitor that affects the differentiation of M1 and M2 macrophages in the tumor microenvironment (TME), and a immune checkpoint inhibitor, nivolumab, that inhibits CTLA4 and PD-1 and ligands in the TME. No genetic testing will be conducted.
- Resected or biopsied tumors that are \geq than 500 mm³ will be collected and cut into two pieces. One piece of tumor will be placed in media, processed and analyzed by flow cytometry (FACS). The second piece will be placed in 10% neutral-buffered formalin and later processed to formalin-fixed paraffin-embedded (FFPE) blocks. Tumors that are \leq 500 mm³ in volume will be not be cut and the whole tumor will be used for FACS analysis.
- For biomarker studies, flow cytometry analysis will be for human CD45, CD3, CD4, CD8, CD56, LAG-3, PD-1 and PD-L1 markers. Cell suspensions will be divided in two tubes, and each tube will be analyzed independently for the individual set of markers. Tube 1: CD45, CD3, CD4, CD8, CD56, PD-1, PD-L1, viability. Tube 2:

CD45, CD3, CD4, CD8, CD56, LAG-3, CD19 or CD20 (B cell marker), TIM3, 4-IBB, and FoxP3 regulatory T cells.

- Histopathologic examination of resected or biopsied tumors will be conducted, the degree of tumor necrosis and mitotic index will be assessed, and immunohistochemical analysis for expression of PD-1, PD-L1, CD8+, CD4+, CD19, CD20, CD45, NK, Ki67, cyclin G1, cyclin D1 will be conducted.
- Storage: Access to stored samples will be limited using a locked freezer. Samples and data will be stored using codes assigned by the investigators. Data will be kept in password-protected computers. Only investigators will have access to the samples and data.
- Tracking: Data will be tracked using a secure database system (e.g. Merge eCOS).
- Disposition at the completion of the study: All stored samples will be archived at the clinical site. Study participants who request destruction of samples will be notified of compliance with such request and all supporting details will be maintained for tracking.

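### The exploratory PTEN endpoint is worded as gene mutation, but the only PTEN assay planned is immunohistochemistry, which measures protein expression

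*Combined protocol and SAP*

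**What the plan says.** Section 2.2.3 lists as an exploratory endpoint "Correlation between DCR and PTEN mutation in patient's archived tumor", and Section 8.1 repeats it. Section 2.1.3 states the matching objective. Section 8.4 gives the analysis: "DCR will be correlated with presence of PTEN mutation in patient's archived tumor and summarized by descriptive statistics". The synopsis says the same under its exploratory objectives, exploratory endpoints and exploratory analysis.

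The assay appears in two places. Table 2 in Section 4 schedules, at screening only, "Immunohistochemistry for PTEN mutation in archived tumor". Section 5.1 lists "Immunohistochemistry for PTEN mutation on patient's archived tumor".

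Section 12.4, on research use of samples and data collected under the protocol, states "No genetic testing will be conducted". Its flow cytometry and immunohistochemistry marker lists do not include PTEN.

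Sections 8.6 and 8.8.1 describe all analyses as descriptive and hypothesis generating.

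**The concern.** The endpoint names a gene-level variable and the plan measures a protein-level one. The two can disagree in both directions: protein may be lost without a mutation, and a mutation may leave staining intact. The plan gives no scoring rule, no cutoff and no rule for inferring mutation from staining, so nothing connects the measured quantity to the named one.

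What is at stake is the meaning of one exploratory result. Section 8.6 says the data should help in planning later Phase 2 trials. Section 1.2.1 says that no clinical study has confirmed the mTOR-pathway biomarkers as predictive, apart from PI3K mutation in some other tumours. A table headed PTEN mutation but filled from staining could therefore lead a later trial to select patients with a test that this trial did not use.

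**Working it through.** The documents state no PTEN prevalence, assay accuracy, power or effect size for this endpoint, so there is no figure of the plan's own to reproduce. The check is a comparison of texts.

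**1. What is named.** Mutation is the variable in seven statements of objective, endpoint or analysis: synopsis exploratory objectives, synopsis exploratory endpoints, synopsis exploratory analysis, and Sections 2.1.3, 2.2.3, 8.1 and 8.4.

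**2. What is measured.** Two statements name an assay, Table 2 and Section 5.1. Both name immunohistochemistry, and both attach the word mutation to it. Total places to correct: 7 + 2 = 9.

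**3. Whether another source supplies mutation status.** None is specified. No section sequences archived tumour, and none collects existing sequencing reports for this endpoint.

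**4. Whether the protocol itself treats the two as different.** It does. Section 1.2.1 puts PTEN in a list of gene mutations and gives phosphorylated-protein expression a separate bullet. Section 12.4 describes its own immunohistochemistry as a reading of marker expression. By the document's own usage, the assay in Section 5.1 yields expression.

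**5. Illustration only.** Suppose mutation is what drives DCR, and that staining errors are unrelated to DCR once mutation status is known. With prevalence p, and sensitivity Se and specificity Sp of staining for mutation:

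- Fraction called abnormal: A = p·Se + (1 − p)(1 − Sp)
- PPV = p·Se / A
- NPV = (1 − p)·Sp / (1 − A)
- Observed DCR difference = true difference × (PPV + NPV − 1)

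The values of p, Se and Sp, and the true 30-point difference, are assumptions and are not in the documents. The plan says "40-50 patients may be enrolled", which supplies the only documented input, N = 40 to 50.

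| p | Se | Sp | A | PPV | NPV | Factor | 30 points would appear as |
|---|---|---|---|---|---|---|---|
| 0.05 | 0.60 | 0.80 | 0.22 | 0.14 | 0.97 | 0.11 | 3.3 |
| 0.10 | 0.80 | 0.80 | 0.26 | 0.31 | 0.97 | 0.28 | 8.4 |
| 0.20 | 0.90 | 0.90 | 0.26 | 0.69 | 0.97 | 0.67 | 20.0 |

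In the middle row A = 0.10 × 0.80 + 0.90 × 0.20 = 0.26. That is 10.4 to 13.0 patients called abnormal, against 4 to 5 truly mutated. The factor runs from 0.11 to 0.67 over these assumptions. This shows only that the label can matter; it does not estimate how much it does. If protein loss rather than mutation drives DCR, staining is the more relevant measure, and the error is purely one of naming.

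**The case against.** The best defence has four parts.

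**Scope of Section 12.4.** A reader might infer that this section forbids sequencing the archived tumour. The text does not go that far. The sentence sits under the intended use of samples and data collected under the protocol, the tissue described there is resected or biopsied tumour, and archived tissue is not mentioned. This part stands. The point does not need Section 12.4, however: without it, immunohistochemistry is still the only PTEN assay in the plan.

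**Existing genetic results.** A reader might infer that mutation status will be unknown for every patient. That is also too strong. Section 3.2 admits "tumors with genetic mutations sensitive to mTOR inhibitors", which implies that some patients arrive with genetic results. But no text collects those results systematically or links them to the PTEN endpoint, so they do not supply it.

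**Surrogate marker.** Staining might be meant as a stand-in for mutation. The plan does not say so and gives no rule for the step from one to the other.

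**Exploratory status.** A reader might expect the trial to claim PTEN mutation as a predictor of DCR. Sections 8.6 and 8.8.1 disclaim firm conclusions, so the documents do not support predicting such a claim. This part stands and limits the severity. It does not make the label correct.

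**Conclusion.** The mismatch is real and rests on the text alone: nine statements say mutation, and the only assay measures protein. It is a minor error in the definition of one exploratory endpoint. The MTD, DCR, PFS, RFS and OS are unaffected.

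The size of any misclassification cannot be stated from the documents, and the attenuation figures rest wholly on assumed inputs and carry no weight for severity. The one premise from outside the plan's wording is that immunohistochemistry does not read gene sequence, and the protocol's own separation of gene mutations from expression markers agrees with it.

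**What to change.** Replace PTEN mutation with PTEN protein expression (lost versus retained) by immunohistochemistry in all nine places:

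- synopsis: exploratory objectives, exploratory endpoints and exploratory analysis
- Sections 2.1.3 and 2.2.3
- Table 2 in Section 4, and Section 5.1
- Sections 8.1 and 8.4

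In Table 2 and Section 5.1 the assay is already named, so only the word mutation changes. Correcting some places and not others would create new contradictions. The background list in Section 1.2.1 concerns gene mutations in the literature and can stay.

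State in Section 8.4, before analysis, the scoring cutoff that separates lost from retained; without it the renamed variable is still undefined. Add that no conclusion about mutation status will be drawn from it. Reporting mutation from sequencing results already on file is not part of this fix, because the plan does not collect them systematically and they would come from a selected subset.

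The cost is text editing plus one scoring rule, with no new assay or tissue. The trial gives up its claim to address PTEN gene mutation, which the planned assay could not support.

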5.2. Treatment Period

All product administration (investigational or otherwise) is to be administered after all other protocol-specified pre-dose assessments have been performed during each visit that it is required. Patients will continue therapy until disease progression or unacceptable adverse events or up to 18 3-week treatment cycles.

5.2.1. Day 1 Assessment

The following assessments will be performed on Day 1 of each cycle, unless otherwise specified:

- Physical examination
- Weight assessment
- BSA calculation (Calculated ONLY on C1/D1; to be recalculated only if the weight changes by > 10% in subsequent cycles)
- Concomitant medication and procedures evaluation
- Vital signs (temperature, systolic and diastolic blood pressure, and pulse)
- ECOG performance status
- Clinical chemistry panel (including but not limited to sodium, potassium, chloride, glucose, alkaline phosphatase (ALP), AST/SGOT, ALT/SGPT, serum albumin)
- CBC, differential and platelet count
- Thyroid function (every 12 weeks)
- Fasting lipids (every 12 weeks)
- Adverse Event assessment

Day 1 evaluations for Cycle 1 may be omitted if screening evaluations are performed within 72 hours of Cycle 1 Day 1. Laboratory assessments: chemistry, hematology,

coagulation, urinalysis, pregnancy test (women of child-bearing potential, includes tubal ligation)

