5.2.3. Day 15 Assessment

The following assessments will be performed on Day 15 of each cycle, unless otherwise specified:

- Concomitant medication and procedures evaluation
- Vital signs
- CBC, differential and platelet count
- Adverse Event assessment

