Skin and Subcutaneous Tissue Disorders	Skin rash	Grade 2	Tolerable: Continue ABI 009 at full dose, monitor as clinically indicated
			Intolerable: Hold ABI-009 until resolution to Grade 1 or baseline and restart at the same dose for 1 st occurrence; for subsequent occurrences, drug will be restarted at a reduced dose; provide supportive care as clinically indicated.
		Grade ≥3	Hold ABI-009 until resolution to Grade 1 or baseline; for subsequent events, drug will be restarted at a reduced dose; provide supportive care as clinically indicated.
Gastrointestinal Disorders	Diarrhea despite optimal medication	Grade 2	Hold ABI-009 until resolution to Grade 1 or baseline and restart at the same dose for 1 st occurrences; for 2 nd and subsequent events, drug will be restarted at a reduced dose; provide supportive care as clinically indicated.
		Grade ≥3	Hold ABI-009 until resolution to Grade 1 or baseline; for subsequent events, drug will be restarted at a reduced dose; provide supportive care as clinically indicated.
Metabolic disorders	Hyperlipemia (cholesterol, triglycerides)	Grade 3	If this is persistent for 2 months, reduce by 1 dose level at start of next cycle

		Grade 4	If this is persistent for 1 month, reduce by 1 dose level at start of next cycle
	Hyperglycemia	Grades 1 and 2	Start at home 2x/day glucose monitoring; initiate medical management
		Grade 3	Initiate medical management ; If recurrent post ABI-009 despite adequate medical management, reduce by 1 dose level
		Grade 4	Initiate medical management, hold ABI-009 until grade 2 or less, restart 1 dose level lower
Hematologic toxicity	Thrombocytopenia, Neutropenia, Anemia	Grade 2	ABI-009 can resume once meeting the following hematological requirements: ANC > 1.5 x 10 ⁹ /L, platelets > 100 x 10 ⁹ /L and hemoglobin ≥9 g/dL
		Grade ≥3	Hold ABI-009 immediately for the remainder of that cycle. Repeat blood collection within 3 days. ABI-009 can resume once meeting following requirements: absolute ANC >1.5 x 10 ⁹ /L, platelet count > 100 x 10 ⁹ /L and hemoglobin ≥9 g/dL. For 2 nd and subsequent events, drug will be restarted at a reduced dose; G-CSF may be given as deemed indicated.

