6.2.2.2. Criteria for Conditional Withholding of ABI-009 Due to Potential Hepatotoxicity

For patients who do not meet the criteria for permanent discontinuation of ABI-009 and have no underlying liver disease, and eligibility criteria requiring normal transaminases and TBL at baseline or patients with underlying liver disease and baseline abnormal transaminases, the following rules are recommended for withholding of ABI-009:

- Elevation of either AST or ALT according to the following schedule:

Baseline AST or ALT value	AST or ALT elevation
Any	> 8x ULN at any time
Any	> 5x ULN but < 8x ULN for \geq 2 weeks
Any	> 5x ULN but < 8x ULN and unable to adhere to enhanced monitoring schedule
Any	\geq 3x ULN with clinical signs or symptoms that are consistent with hepatitis (such as right upper quadrant pain/tenderness, fever, nausea, vomiting, jaundice).

- OR: TBL $>$ 3x ULN at any time
- OR: ALP $>$ 8x ULN at any time

ABI-009 should be withheld pending investigation into alternative causes of DILI. Rechallenge may be considered if an alternative cause for impaired liver tests (ALT, AST, and ALP) and/or elevated TBL is discovered and the laboratory abnormalities resolve to normal or baseline.

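### The 12-week fasting-lipid schedule does not supply the values that Table 5's 1- and 2-month hyperlipemia rules and the two-dose DLT look rely on; Section 5.2.3 also omits the Day 15 chemistry in Table 2

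*Combined protocol and SAP*

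**What the plan says.** **Lipid schedule.** Section 5.2.1 lists "Fasting lipids (every 12 weeks") among the Day 1 assessments. Table 2 footnote c, attached to the Day 1 column, allows Cycle 1 Day 1 evaluations to be skipped after recent screening, "except for thyroid and fasting lipids every 12 weeks". Table 3 puts total cholesterol, HDL, LDL and triglyceride under Other Labs, not under Chemistry, so the routine panel does not supply them.

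**Lipid rules.** Under metabolic disorders, Table 5 (Section 6.2.1) says for Grade 3 hyperlipemia: "If this is persistent for 2 months, reduce by 1 dose level at start of next cycle". For Grade 4 it says: "If this is persistent for 1 month, reduce by 1 dose level at start of next cycle". No passage provides a repeat lipid draw after an abnormal value.

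**DLT and escalation.** The note in Section 2.3 counts any Grade 3 or higher non-hematologic toxicity as a DLT and does not exempt lipid values. Escalation is permitted if no DLT has occurred after 2 doses. ABI-009 starts on Day 8 of Cycle 2 (Section 6.1).

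**Day 15 chemistry.** The "Clinical Chemistry Panel" row of Table 2 is marked at screening, Days 1, 8 and 15, and end of treatment. Section 5.2.2 lists the panel for Day 8. Section 5.2.3 opens "The following assessments will be performed on Day 15 of each cycle, unless otherwise specified" and then lists only concomitant medication and procedures, vital signs, blood counts and adverse events.

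**The concern.** A rule that acts on persistence needs at least two values spaced no further apart than the persistence period. Here the spacing is 84 days and the periods are 1 and 2 months, so a site that follows the schedule exactly cannot apply a written safety rule when it falls due.

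The same schedule bears on the MTD, the only primary endpoint. A laboratory toxicity can count as a DLT only if someone measures it, and the lipid schedule has no draw in the window that decides escalation. Lipid toxicity is one the protocol expects. Section 1.2.1 cites 6% Grade 3 or 4 hypertriglyceridemia with rapamycin and rapalogs, Section 1.2.4 cites 15% hypertriglyceridemia of any grade in the earlier ABI-009 study, and Section 3.2 sets entry limits for triglyceride and cholesterol.

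The Day 15 discrepancy matters because the hepatic withholding rule in Section 6.2.2.2 (for AST or ALT, "> 8x ULN at any time") and the hyperglycemia rules in Table 5 use chemistry values. The two visit descriptions set different pre-dose requirements for the second ABI-009 infusion of each cycle.

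**Working it through.** The plan states no figure to reproduce on this point; the check is schedule arithmetic. It assumes 21-day cycles without delay, the 12-week interval counted from Cycle 1 Day 1, and 1 month = 30.4 days.

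**Formula.** Study day of Cycle c Day y = 21 × (c − 1) + y.

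**Step 1: ABI-009 doses.** Cycle 2 Day 8 = 21 + 8 = Day 29. Cycle 2 Day 15 = 21 + 15 = Day 36.

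**Step 2: scheduled lipid draws.** Day 1 + 84k gives Days 1, 85, 169, 253 and 337, which are Day 1 of Cycles 1, 5, 9, 13 and 17.

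**Step 3: first scheduled lipid value on ABI-009.** This is Day 85: 85 − 29 = 56 days after dose 1 and 85 − 36 = 49 days after dose 2. Doses already given: Cycles 2 to 4, 3 × 2 = 6.

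**Step 4: next scheduled value.** This is Day 169, 84 days after Day 85. Doses in between: Cycles 5 to 8, 4 × 2 = 8.

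| Table 5 rule | Persistence period | Scheduled spacing | Excess |
|---|---|---|---|
| Grade 4 | 1 month, about 30.4 days | 84 days | 84 − 30.4 = 53.6 days |
| Grade 3 | 2 months, about 60.9 days | 84 days | 84 − 60.9 = 23.1 days |

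**Step 5: the escalation look.** If the 2 doses are ABI-009 doses, a patient reaches the look on Day 36, with no lipid draw scheduled from Day 29 to Day 36. If they were nivolumab doses, the second is Cycle 2 Day 1 = Day 22, before any ABI-009. Neither reading places a scheduled on-ABI-009 lipid value at that point.

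**Step 6: possible size for the DLT rule (assumption).** The documents give no rate of Grade 3 or higher lipid events within the DLT window. If it were 2% to 6% per patient, the chance that a three-patient cohort contains at least one would be 1 − 0.98³ = 5.9% to 1 − 0.94³ = 16.9%. One DLT among three changes the decision from escalating to expanding to six patients. The upper value borrows the 6% cited for rapalogs, which is not specific to this window.

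**Step 7: chemistry around the first two ABI-009 doses.**

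| Source followed | Panel days | Largest gap |
|---|---|---|
| Table 2 | 22, 29, 36, 43 | 7 days |
| Sections 5.2.1 to 5.2.3 | 22, 29, 43 | 14 days |

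Under Section 5.2.3 the Day 36 infusion has no same-day scheduled panel. Both sources have a panel on Day 43, 7 days after dose 2.

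**The case against.** The best defence is that a schedule is a minimum. Nothing forbids unscheduled tests. Section 9.2 provides for monitoring adverse events through laboratory findings, Section 9.3 asks for onset and resolution dates, and Section 12.6 allows collected blood to be used for tests needed to limit patient risk. A clinician who sees a Grade 4 lipid result is unlikely to wait 84 days. This stands. A reader might infer that the Table 5 rules can never operate before Day 169; the documents support only that the schedule does not provide the values earlier. The defence does not cover the first detection, because until Day 85 no scheduled result exists to prompt a retest.

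A reader might also infer that Table 2 contradicts Section 5.2.1 by marking lipids on Day 1 of every cycle. It does not: footnote c qualifies that column, and both places say 12 weeks.

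On Day 15, the opening of Section 5.2.3 yields to anything specified elsewhere, Table 2 "outlines the specific time points for study assessments", and Section 5.2 requires all protocol-specified pre-dose assessments before dosing. It would therefore be too strong to say that half of all ABI-009 infusions go without a liver or glucose check; that follows only where a site works from Section 5.2.3 and not Table 2. Nor could a pre-dose sample on Day 36 show toxicity from dose 2. The Day 43 panel can do so under either text.

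Finally, the expected frequency may be low. In the earlier ABI-009 study most events in the group that included hypertriglyceridemia were Grade 1 or 2, and at 100 mg/m² (7 patients) the only event in that group was a Grade 3 anemia. Section 1.2.4 reports hypertriglyceridemia among hematologic events, whereas Table 5 calls it metabolic. If it were treated as hematologic, only Grade 4 would be a DLT. This limits the size of the problem but leaves the mismatch in place.

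**Conclusion.** The point holds. The 84-day lipid spacing overshoots the Table 5 periods by about 54 and 23 days. The first scheduled on-ABI-009 value follows 6 doses, with 8 more before the next. No lipid value is scheduled between the first ABI-009 dose and the two-dose look, so lipid DLTs are not systematically ascertained when the MTD is set.

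It would go too far to conclude that the MTD will be set with no lipid event seen. Unscheduled tests may reveal one, and in a slowly filled cohort an early patient could reach Day 85 before the last patient completes two doses.

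The Day 15 item is a smaller, separate inconsistency, with consequences only where Section 5.2.3 is followed over Table 2.

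Besides the timing assumptions in the working, the DLT part assumes that lipid events count as non-hematologic, as their place in Table 5 suggests. The Table 5 dose rules themselves are not questioned.

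**What to change.** Three sets of passages must be reconciled, so that each stated rule has the scheduled values it relies on:

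- the lipid interval in Section 5.2.1 and Table 2 footnote c with the persistence periods in Table 5;
- the lipid schedule with the DLT definition and the timing of escalation in Section 2.3 and the synopsis;
- the Day 15 list in Section 5.2.3 with the chemistry row of Table 2.

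The sponsor decides which passage changes in each case; no dose rule or sampling interval is proposed here. The cost is mainly an amendment to wording. If the sponsor chooses more frequent lipid sampling, the burden is extra fasting samples, which could be taken at visits where blood is already drawn. Day 15 chemistry already stands in Table 2, so aligning the two texts need not add to the planned tests.
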